6.4.2 Secondary Efficacy Analysis

Overall Survival (OS)

OS is the key secondary efficacy endpoint and is defined as the time from randomization to death due to any cause.

A stratified log-rank test incorporating the randomized stratification factors (region, ECOG performance status) will be used to compare treatment groups. The HR and its 2-sided 95% CI will be estimated using the stratified Cox-proportional hazards model. The median and other quartiles of OS for each treatment group will be estimated using the Kaplan-Meier method and the 95% CI will be calculated using the Brookmeyer-Crowley method (Brookmeyer and Crowley, 1982). Kaplan-Meier curves for OS will also be generated and plotted over time to provide a visual description of the OS change over time.

OS data will be censored at the date that the patient was last known to be alive before the date of data cutoff. For patient who died and have last known alive date after the date of data cutoff, OS data will be censored at the date of data cutoff. Analysis will be conducted by using the ITT Analysis Set.

Time to second subsequent treatment (TSST)

TSST is defined as the time from randomization until the second subsequent anticancer therapy or death. The second subsequent anticancer therapy should be conditional on the first anticancer therapy and on or after date of PD from the first anticancer therapy. Patients alive and without the second anticancer therapy, or alive with the second anticancer therapy but no PD from the first anticancer therapy will be censored at last known alive. Details of the censoring rule are specified in Table 2.

If data collected is deemed as suffice, TSST will be assessed using a stratified log-rank test incorporating the randomized stratification factors (region, ECOG performance status) in ITT Analysis Set. The HR and its 2-sided 95% CI will be estimated using the stratified Cox-proportional hazards model. The median and other quartiles of TSST for each treatment group will be estimated using the Kaplan-Meier method and the 95% CI will be calculated using the Brookmeyer-Crowley method (Brookmeyer and Crowley, 1982). Analysis will be conducted by using the ITT Analysis Set.

Table 2. Censoring Rules for Analysis of TSST

No.	Situation	Date of Progression or Censoring	Outcome
1	Death	Death Date	Event
2	Second subsequent anticancer therapy	Second subsequent anticancer therapy start date	Event

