6.5.2 Adverse Events

AEs will be graded by the investigators using NCI CTCAE v4.03. The AE verbatim descriptions (investigator terms from the CRF) will be classified into standardized medical terminology using the Medical Dictionary for Regulatory Activities (MedDRA). Adverse events will be coded to the MedDRA (Version 22.0 or higher) lower level term closest to the verbatim term. The linked MedDRA preferred term (PT) and primary system organ class (SOC) are also captured in the database.

A treatment-emergent adverse event (TEAE) is defined as an AE that had an onset date on or after the date of the first dose of study treatment through 30 days after the last dose (permanent discontinuation of study treatment) or initiation of new anticancer therapy. Only those AEs that were treatment emergent will be included in summary tables. All AEs, treatment emergent or otherwise, will be presented in patient data listings.

An overview table of patients with at least one TEAE will be presented, as the number (percentage), with the incidence of following:

- patients with any TEAE
- patients with any TEAE with Grade 3 or higher
- patients with any serious TEAE
- patients with any TEAE leading to death
- patients with any TEAE leading to treatment discontinuation
- patients with any TEAE leading to dose modification
 - patients with any TEAE leading to dose interruption
 - patients with any TEAE leading to dose reduction
- patients with any treatment-related TEAE
- patients with any treatment-related TEAE with Grade 3 or higher
- patients with any treatment-related serious TEAE

- patients with any treatment-related TEAE leading to death
- patients with any treatment-related TEAE leading to treatment discontinuation
- patients with any treatment-related TEAE leading to dose modification
 - patients with any treatment-related TEAE leading to dose interruption
 - patients with any treatment-related TEAE leading to dose reduction

Summaries of all above TEAEs will also be reported as the number (percentage) of patients by SOC and PT.

Summaries of all TEAEs, SAE, Grade 3 or higher TEAEs, treatment-related TEAEs, and TEAE leading to treatment discontinuation will also be provided by PT only in descending order of frequency.

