9 REFERENCES

- Clopper, C. and Pearson, ES. The use of confidence or fiducial limits illustrated in the case of the binomial, *Biometrika* 1934;26: 404-413.
- Collett D. *Modelling survival data in medical research*. New York: Chapman & Hall; 1994.
- Common Terminology Criteria for Adverse Events (CTCAE). Version 4.0. United States Department of Health and Human Services, National Institutes of Health, National Cancer Institute, Washington, DC, USA, May 28, 2009.
- Greenwood M. "The natural duration of cancer". *Reports on Public Health and Medical Patients* (London: Her Majesty's Stationery Office). 1926; 33:1-26.

10 APPENDIX**10.1 HANDLING OF PARTIALLY MISSING DATES****1) Adverse Events**

The imputation rule for the safety analyses will be used to address the issues with partial dates. When the start date or end date of an adverse event is partially missing, the date will be imputed to determine whether the adverse event is treatment-emergent. When in doubt, the adverse event will be considered treatment emergent by default. The following rules will be applied to impute missing or partial dates for adverse events:

	Missing	Impute	Exception
Start Date	Day	01	If Month and Year = Month and Year of treatment start date, then set to treatment start date
	Day/Month	January 01	If Year = Year of treatment start date, then set to treatment start date
	Day/Month/Year or Year only	Do not impute	N/A
End Date	Day	Last day of the month	N/A
	Day/Month	December 31	N/A
	Day/Month/Year or Year only	Do not impute	N/A

If the imputed AE start date becomes after AE end date, then update AE start date same as AE end date. And if the imputed start date or end date becomes after death date, then set to death date.

The following rule will be applied to impute missing toxicity grade of AE:

1. The highest grade will be used from patient's AEs with the same preferred term.
2. If patient has no AEs with the same preferred terms, the highest grade of the AEs with the same SOC will be used.
3. If patient has no same SOC, the highest grade of all AEs from that patient will be used.

4. If it is the single AE reported for that patient, no imputation for the missing grade will be done.

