2) Prior/Concomitant Medications, Disease and Medical History, Prior Therapy (Drug, Surgery/Procedure, Radiotherapy)

	Missing	Impute	Exception
Start Date	Day	01	N/A
	Day/Month	January 01	N/A
	Day/Month/Year or Year only	Do not impute	N/A
End Date	Day	Last day of the month	N/A
	Day/Month	December 31	N/A
	Day/Month/Year or Year only	Do not impute	N/A

For concomitant medications; if the imputed start date or end date becomes after death date, then set to death date.

For disease history and prior therapy, including initial diagnosis date, relapse date, therapy date (start/end date), or surgery date; if the imputed start date or end date becomes after first dose date, then set to first dose date - 15.

3) Initial Diagnosis, Metastatic Disease, and Most Recent Progression

	Missing	Impute	Exception
Initial Diagnosis Date/ Metastatic Disease Date/ Most Recent Progression Date	Day	01	N/A
	Day / Month	January 01	N/A
	Day / Month / Year or Year only	Do not impute	N/A

If the imputed initial diagnosis date, metastatic disease date or most recent progression date is on or after the treatment start date, then set to treatment start date - 1.

4) Death

In case complete death dates are not recorded, impute as follows:

[figure not shown]
- If both month and day are missing, then the imputed month and day will be 01Jan or the last date of patient known to be alive + 1, whichever is later.
- If only day is missing, the death will be assumed to be on the first day of the month or the last date of patient known to be alive +1, whichever is later.

5) New Anticancer Therapy

If the start day of a subsequent anticancer therapy is incomplete or missing, impute as follows:

- If both month and day are missing,
 - 1) impute the date as 31Dec, if the year is earlier than the year of the first PD date + 1 or the treatment end date + 1, whichever is later.
 - 2) impute the date as 01Jan, if the year is later than the year of the first PD date or the treatment end date + 1, whichever is later.
 - 3) impute the date as the first PD date + 1 or the treatment end date + 1, whichever is later, if the year is the same year of first PD date + 1 or the treatment end date + 1, whichever is later.
- If only day is missing,
 - 1) impute the date as the first day of the month if year and month are available and partial new anticancer therapy date still could indicate it is at least one month later than the first PD date +1 or the treatment end date +1, whichever is later.

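### SAP 10.1(5) dates incompletely recorded subsequent therapies without regard to their order, so a TSST event can be mistimed or lost and the TEAE window can close one day after last dose

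*SAP*

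**What the plan says.** SAP Appendix 10.1, item 5, opens with "If the start day of a subsequent anticancer therapy is incomplete or missing, impute as follows". It does not separate the first subsequent therapy from later ones. Its one anchor is the later of first PD + 1 day and treatment end + 1 day. The branches that matter here are:

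- Month and day missing, recorded year equal to the anchor's: "impute the date as the first PD date + 1 or the treatment end date + 1, whichever is later".
- Month and day missing, later year: "impute the date as 01Jan, if the year is later than the year of the first PD date".
- Day missing, later month: "impute the date as the first day of the month if year and month are available".
- Day missing, same month and year as the anchor: the anchor date.

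Earlier years or months go to 31 December or to the last day of the month.

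Two analyses use these dates. For TSST, SAP 6.4.2 states: "The second subsequent anticancer therapy should be conditional on the first anticancer therapy and on or after date of PD from the first" therapy. A living patient who does not meet this is censored at the date last known alive. Table 2 row 2, however, counts the start of the second therapy as the event and does not repeat the condition.

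For safety, SAP 6.5.2 runs the TEAE window from first dose "through 30 days after the last dose (permanent discontinuation of study treatment) or initiation of new anticancer therapy". Protocol 10.6.2 makes clear that the earlier of the two ends it. Only TEAEs enter the summary tables; all AEs are listed.

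**The concern.** The anchor suits a first subsequent therapy, which normally starts after progression or after study drug ends. It does not suit a second one, which must come after the first. Other items in the same appendix do respect order: an imputed death cannot precede the day after the patient was last known alive, and an imputed AE start cannot pass the AE end. Item 5 has no such floor, although SAP 6.3.9 already uses a sequence/regimen number for post-treatment therapies.

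TSST is a listed secondary endpoint whose event date is the date being imputed. Further therapy is learned through contact about every 12 weeks, by telephone or other means (protocol 5.6.2), which is a plausible source of partial dates. On the safety side, the same-month and same-year branches choose the earliest date the rule allows for the new therapy, and that shortens the TEAE window.

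**Working it through.** The plan gives no figure for this point to reproduce. All calendar dates below are assumed, because the documents contain no patient dates and no rate of partial dates. Treatment end is taken as the date of last dose. Durations use end date − start date + 1, as for study day in SAP 6.2.1.

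**1. Year-only second therapy, same year as the anchor**

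- Randomization 1 Oct 2018; first PD 18 Mar 2019; treatment end 20 Mar 2019.
- First subsequent therapy 10 Apr 2019; PD on it 20 Aug 2019.
- Second therapy truly 5 Sep 2019, recorded only as 2019.
- Anchor = later of 19 Mar and 21 Mar = 21 Mar 2019, so the second therapy is imputed to 21 Mar 2019.
- This is 20 days before the first therapy and 168 days before the true start.
- True TSST = 339 + 1 = 340 days. Imputed TSST = 171 + 1 = 172 days. Difference = 168 days.

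Outcome by governing text: under Table 2 row 2, an event at day 172. Under 6.4.2, 21 Mar precedes PD on the first therapy (20 Aug), the condition fails, and a living patient is censored although the event occurred.

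The extreme of this branch is PD and treatment end on 1 Jan, anchor 2 Jan and true start 31 Dec of the same year, which is 363 days early.

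**2. Year-only second therapy, later year**

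First PD 10 Dec 2018, treatment end 12 Dec 2018, first therapy 15 Jan 2019, second recorded as 2019. It is imputed to 1 Jan 2019, 14 days before the first therapy.

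**3. Only the day missing**

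With the dates of case 1 and the second therapy recorded as Sep 2019, the imputed date is 1 Sep 2019: 4 days early and still after the first therapy. The order is broken only if both therapies start in the same month.

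**4. How often order breaks, given that a date is partial**

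Simulation of 100,000 second-therapy dates per setting. Assumptions: PD uniform over a year, anchor = PD + 1, first therapy 2–6 weeks after PD, exponential gap from first to second therapy.

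| Median gap (months) | Year-only: in the PD year | Year-only: imputed on or before first therapy | Year-only: mean error (months early) | Day-only: imputed on or before first therapy |
|---|---|---|---|---|
| 3 | 59% | 66% | 3.4 | 11% |
| 4 | 51% | 57% | 3.8 | 8% |
| 5 | 45% | 51% | 4.1 | 7% |
| 6 | 40% | 46% | 4.4 | 6% |

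For day-only dates the mean error is about 15 days. These shares are conditional on a date being partial; they are not shares of all patients.

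**5. TEAE window**

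Window end = earlier of last dose + 30 days and the imputed start of new therapy. Last dose is 5 Mar 2019, so the 30-day limit is 4 Apr 2019.

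| First PD | New therapy recorded as | Imputed start | Days from last dose to window end |
|---|---|---|---|
| 4 Mar | Mar 2019 | 6 Mar | 1 |
| None | Mar 2019 | 6 Mar | 1 |
| 4 Mar | 2019 | 6 Mar | 1 |
| 25 Mar | Mar 2019 | 26 Mar | 21 |
| 4 Mar | Apr 2019 | 1 Apr | 27 |

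The no-PD row assumes that the anchor is then treatment end + 1, which the rule does not spell out. The latest date compatible with Mar 2019 is 31 Mar, day 26; with 2019 alone, the 30-day limit applies. So the severe shortening needs a partial date in the anchor's month or year and PD that is absent or not after treatment end.

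**The case against.** Much of the case against a stronger claim stands.

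- A reader might infer that every subsequent therapy is redated. Complete dates are untouched, and only the same-year and same-month branches assign the anchor itself.
- A reader might infer false TSST events. The second therapy did take place, so the event is mistimed under Table 2 row 2 or lost under the 6.4.2 text; neither route invents one.
- A reader might infer that TSST is systematically shortened. That holds only if Table 2 row 2 governs. Under 6.4.2 the patient is censored at last known alive, usually a later date.
- A reader might infer a contradiction with the sentence "When in doubt, the adverse event will be considered treatment emergent by default". That sentence sits in the item on adverse events and deals with partial AE dates. It does not address a fully dated AE that falls after an imputed therapy start.

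The stakes are also limited. TSST is analysed only if the data are judged sufficient, there is no multiplicity adjustment, the rule is the same in both arms, and no between-arm bias has been shown. AEs outside the window remain in the listings, and SAP 6.5.3 summarizes all deaths.

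None of this removes the defect. Nothing else in the SAP stops an imputed second therapy from preceding the first, and 6.4.2 and Table 2 treat such a date differently.

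**Conclusion.** The point holds in a limited form. Item 5 of SAP 10.1 ignores therapy order, so a second subsequent therapy recorded by year only can be placed before the first. Its TSST event is then too early or is lost to censoring, depending on which part of 6.4.2 is programmed. Under the assumed intervals above, 46–66% of year-only second-therapy dates would be imputed on or before the first therapy, with a mean error of 3.4–4.4 months; day-only dates are much less affected.

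Separately, a partial date for the first new therapy can end the TEAE window one day after last dose instead of up to 30, in the direction that counts fewer events. How many patients either problem would touch cannot be stated, because the documents give no rate of partial dates. The primary PFS sample size does not depend on this rule.

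**What to change.** 1. In SAP 10.1(5), floor the imputed date of each second or later therapy by regimen sequence: not before the day after the start of the preceding therapy, nor before PD on that therapy if recorded, and within the known month or year.
2. Reconcile Table 2 row 2 with the 6.4.2 condition, so that one rule decides whether a second therapy counts as an event.
3. For the TEAE cut-off only, use the latest start of new therapy compatible with the partial date, capped at last dose + 30 days.

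The cost is a few sentences and a small programming change. A few more AEs may count as treatment emergent. Some early bias in TSST remains when neither PD nor an end date is recorded for the first therapy, because the floor is then the day after that therapy started.
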